### 3.1.6 Treatment Windowing for “As-Treated” Summaries

This section describes how treatment (infusion duration) will be assigned to study results for “as-treated” summaries (if warranted) and for AE listings, using the safety analysis set.

#### Results collected at a particular study visit:

- Results in the MTX Run-in Period and for Day 1 should always be corresponding to the assigned treatment group.
- Pre-infusion results after Day 1 should correspond to the treatment given at the prior visit. For example, if a subject took 60-min infusion at Day 1, but then attended their Week 2 visit and had a 120-min infusion done, then their Week 2 pre-infusion results would correspond to the 60-min treatment group and their Week 4 visits would correspond to the >60-min treatment group.
- Post-infusion results should correspond to the actual treatment given at the visit. E.g. using the same example as above, if 120-min infusion was given at Week 2, then post-infusion results should correspond to > 60-min treatment group.
- Results at Week 24 and at end of pegloticase infusion should correspond to the last treatment that a subject took.
- Follow-up results will correspond to the last treatment that a subject took.

### 3.1.7 Handling Rules for sUA Values

For the determination of sUA responder endpoints, scheduled assessments of sUA and unscheduled assessments of sUA, reported by the central laboratory, will be used. Local

laboratory-processed pre-infusion sUA results will be used only when the central laboratory-processed value at a time point is not available, but the local lab-processed pre-infusion value, collected value at the same time point, is available.

When the central laboratory or local laboratory reports a value for sUA as being lower than or lower than and equal to the lab assay's limit of quantification (e.g. “<0.02” or “<= 0.02”), zero will be used as the numeric value for the purpose of determining response and for summaries of observed values and the change from baseline. When the central laboratory or local laboratory reports a value for sUA as being higher than or higher and equal to a certain value of quantification (e.g. “>8.7”, “>= 8.7”), the numeric value (e.g. 8.7) after ‘>’ or “>=” is used for the purpose of determining response and for summaries of observed values and the change from baseline

Unscheduled sUA visits, assessed by the central laboratory or local laboratory, will be assigned an analysis window according to the tables above in Visit Windowing ([Section 3.1.5](#)). These unscheduled visits will be used for the determination of sUA responder.

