## 7.2 Rationale for this Study

Pegloticase (KRYSTEXXA, a recombinant modified mammalian urate oxidase [uricase]), is approved by the United States FDA and the European Commission for use in patients with gout, at a dose of 8mg IV every two weeks. Pegloticase is efficacious in reducing sUA levels and improving clinical signs and symptoms of gout. Pegloticase provides medical benefits by lowering sUA and eliminating tophi in patients who currently have no therapeutic options. The pooled response rate for pegloticase 8 mg at 6 months is 42%, based on at least 80% of the sUA values being less than 6 mg/dL at both the 3 month and 6 month time points, with placebo response rates of 0%, a difference that was clinically important and statically significant.

Currently, pegloticase is FDA approved for intravenous administration over no less than 120 minutes [KRYSTEXXA Full Prescribing Information]. Pegloticase needs to be re-administered every two weeks to achieve optimal therapeutic outcomes and prevent elevations in sUA levels and reduce tophus burden [Baraf 2013]. Compliance with such a regimen can be burdensome and pose a barrier to treatment for some patients who may otherwise benefit from the infusion. Therefore, there is an unmet need for patients with uncontrolled gout to have access to a therapy that is effective with limited AEs, amenable to high patient compliance over several months. Administering pegloticase over a shorter duration time may address this unmet need.

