### **9.5.10 Restricted Medications**

Subjects should not receive the following medications from the time of Screening through the end of pegloticase and MTX treatment:

- Oral urate-lowering therapies including allopurinol, febuxostat, probenecid, lesinurad, or other ULT for gout; re-introduction of oral ULTs should not start until after the End of Pegloticase Visit (or End of Study) laboratory tests are collected.
- Any PEG-conjugated drug
- Any other investigational agent
- Methotrexate (other than study investigational product), azathioprine, mycophenolate mofetil, or other systemic immunosuppressants aside from glucocorticoids for gout flare prophylaxis (< 10 mg prednisone or equivalent per day) or intermittent gout flare treatment
- If a subject is treated with antibiotics, refer to Section 9.5.7.3.2.2.
- Systemic immunosuppressive agents

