#### 3.1.1 Reporting Conventions

The formats for the tables, listings, and figures described in this SAP will be provided in a companion document. Changes to the formats of these reports that are decided after the finalization of the SAP will not require an amendment. In addition, any additional supportive or exploratory analyses requested after SAP approval will not require amendment of the SAP. These additional analyses will be described in the CSR.

Study data from the electronic case report forms as well as relevant derived variables will be provided in subject data listings. An indication of specific listings for each data type may be indicated in the text of subsequent SAP sections. Data listings supplied as part of the CSR will be sorted by study center number concatenated with subject number, assessment dates, and time point, if collected.

The following conventions will be applied to all data presentations and analyses:

Continuous variables will generally be summarized by the number of subjects, mean, standard deviation, median, minimum, and maximum. Unless otherwise specified, the minimum and maximum values will be displayed to the same number of decimal places as the raw data, the mean and median will be presented to one extra decimal place compared to the raw data, and the standard deviation will be displayed to two extra decimal places compared to the raw data

Categorical variables will be summarized using frequencies and percentages within each category. Unless otherwise specified, the percentage will be presented in parentheses to one decimal place. Frequency and percentage values of 0 will be presented as '0' rather than '0 (0)'.

Unless otherwise specified, time to event data will be reporting using weeks as the timescale.

All summary tables will include the analysis set sample size (i.e., number of subjects).

Date variables will be formatted as DDMMYY for presentation.

Unless otherwise specified, confidence intervals (CI) will be based on two-sided 95% confidence.

If multiple assessments occur at a given post-baseline time point, the latest value will be used.

There will be no statistical testing to make an inference.

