### 3.1.5 Visit Windowing

For all analyses, data will be summarized according to the scheduled visit and time points as outlined in the protocol and by the visit denoted on the electronic case report form (eCRF). The reference date associated with each visit is collected on the Visit Date eCRF page. Further, the End of Study/Early Termination (ET) visit and the End of Pegloticase Infusion Visit will be windowed to a visit based on the study day of occurrence relative to the target day of each scheduled visit according to Tables 1-8 below.

**Table 1: Visit Windows for Assigning End of Study/ET and End of Pegloticase Visits to a Scheduled Visit (Vital Signs, sUA)**

Study Period	Visit	Target Day a	Window for Reassignment to Scheduled Visit (days)
Pegloticase + MTX	Day 1	1	1
	Week 2	15	2 – 22
	Week 4	29	23 – 36
	Week 6	43	37 – 50
	Week 8	57	51 – 64
	Week 10	71	65 – 78
	Week 12	85	79 – 92
	Week 14	99	93 – 106
	Week 16	113	107 – 120
	Week 18	127	121 – 134
	Week 20	141	135 – 148
	Week 22	155	149 – 162
	Week 24	169	≥ 163

a Study days in the Pegloticase + MTX Period will be calculated relative to the first dose of Pegloticase.

**Table 2: Visit Windows for Assigning End of Study/ET and End of Pegloticase Visits to a Scheduled Visit (Laboratory Assessments and Urine Albumin: Creatinine Ratio)**

Study Period	Visit	Target Day a	Window for Reassignment to Scheduled Visit (days)
Pegloticase + MTX	Day 1	1	1
	Week 2	15	2 – 29
	Week 6	43	30 – 71
	Week 14	99	72 – 127
	Week 22	155	128 – 162
	Week 24	169	≥ 163

a Study days in the Pegloticase + MTX Period will be calculated relative to the first dose of Pegloticase.

[figure not shown]
**Table 3: Visit Windows for Assigning ET and End of Pegloticase Visits to a Scheduled Visit (Pegloticase PK and Antibody testing)**

Study Period	Visit	Target Day a	Window for Reassignment to Scheduled Visit (days)
Pegloticase + MTX	Day 1	1	1
	Week 2	15	2 – 29
	Week 6	43	30 – 64
	Week 12	85	65 – 113
	Week 20	141	114 – 155
	Week 24	169	≥ 156

a Study days in the Pegloticase + MTX Period will be calculated relative to the first dose of Pegloticase.

**Table 4: Visit Windows for Assigning ET and End of Pegloticase Visits to a Scheduled Visit (Pre-infusion MTX Polyglutamate PK)**

Study Period	Visit	Target Day a	Window for Reassignment to Scheduled Visit (days)

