### 3.4.2 Secondary Endpoint Analyses

#### 3.4.2.1 Month 6 Responders

The estimand for the secondary endpoint for Month 6 responders is defined by the following:

Population	Modified Intent-to-Treat Analysis Set for the cohort chosen to be most desirable for infusion
Endpoint	Proportion of responders during Month 6
ICE	Early discontinuation of pegloticase; meeting sUA discontinuation criterion (sUA values > 6 mg/dL at 2 consecutive scheduled visits [excluding post-infusion sUA] starting at Week 2)
ICE Strategy	Participants who meet the sUA discontinuation criterion, or have < 2 sUA from separate visits available during Month 6 are considered treatment failures (non- responders). Available sUA results during Month 6 from participants who discontinue pegloticase for reasons other than meeting the sUA discontinuation criterion prior to Week 24 will be used in the response calculation.
Population-level Summary	Proportion of subjects who meet the response definition during Month 6

The proportion of responders during Month 6 will be summarized, along with a two-sided 95% exact (Clopper-Pearson) confidence interval for the proportion. A responder is defined as a subject for whom the proportion of time that the sUA-time curve is  $<6$  mg/dL during Month 6 (Weeks 20, 22 and 24) is at least 80%. The proportion of time that the sUA level is below 6 mg/dL is defined as the ratio of the time during which the sUA level remains below 6 mg/dL (using linear interpolation, if necessary) to the entire time interval during Month 6. Any unscheduled sUA collection during Month 6 will be included. Subjects with only one visit for sUA collection within the period will be considered non-responders, regardless of the value(s) of at the visit.

The number and proportion of subjects meeting the Individual Subject sUA Discontinuation Criteria will be summarized descriptively as part of the secondary endpoints.

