### 3.4.3 Exploratory Endpoint Analyses

## 3.5 Analysis of Pegloticase Pharmacokinetics, Methotrexate Polyglutamates, and Anti-Drug Antibodies

### 3.5.1 Pegloticase and MTX PK

Serum samples for pegloticase PK analysis will be collected approximately 15 minutes to 2 hours after the end of infusion on Day 1; prior to infusion and approximately 15 minutes to 2 hours after the end of the infusion at Weeks 2, 6, 12 and 20. An additional PK sample will be collected at the End-of-Study (Week 24)/Early Termination Visit.

PK summaries will be done for the PK analysis set. MTX polyglutamate summaries will be done for the mITT analysis set. All results will be presented by 'as assigned' infusion duration group.

The following presentations of subject serum pegloticase concentration data covered in this SAP will be provided for pegloticase:

- A listing including subject, week/time point (actual, planned), treatment and serum concentrations. End of infusion sampling times are expressed relative to the start time of infusion.
- A table summary of serum pegloticase concentrations at each time point (n; mean, SD, coefficient of variation (CV)% calculated as  $100\% \times SD/mean$ , minimum, 25th percentile, median, 75th percentile, maximum, geometric mean and geometric CV%) will be provided for the PK analysis set. Similar tables will be produced by Month 6 sUA responder status.

Further, the mean and CV% of pegloticase concentrations will be provided by visit in the subset of subjects who are ADA positive (defined as positive for anti-PEG or anti-uricase antibodies at any visit) and ADA negative (defined as negative for both anti-PEG and anti-uricase antibodies at all visits) for each visit.

All concentrations BLQ after the first pegloticase infusion will be imputed by half of LLOQ for the analysis summaries. The number of BLQ records will be summarized. Concentrations more than 17 days after the last infusion will be excluded from the summary.

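### The SAP does not settle which sUA values decide Month 6 response: the Week 24 window has no end, and restarted oral urate-lowering therapy has no rule

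*SAP*

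**What the plan says.** SAP 3.4.2.1 takes Month 6 as Weeks 20, 22 and 24. A responder has a linearly interpolated sUA curve below 6 mg/dL for at least 80% of that interval. No calendar end to the interval is given.

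**Which values fall in Month 6**
- SAP 3.1.5: "the End of Study/Early Termination (ET) visit and the End of Pegloticase Infusion Visit will be windowed to a visit based on the study day". Table 1 is titled "Visit Windows for Assigning End of Study/ET and End of Pegloticase Visits to a Scheduled Visit (Vital Signs, sUA"). Its windows for Weeks 4 to 22 are each 14 days wide. Week 24 is Day 163 or later, with no end.
- SAP 3.1.7: "Unscheduled sUA visits, assessed by the central laboratory or local laboratory, will be assigned an analysis window according to the tables above". It adds that these values feed responder status.
- SAP 3.4.2.1: "Any unscheduled sUA collection during Month 6 will be included".
- SAP 3.1.1: "If multiple assessments occur at a given post-baseline time point, the latest value will be used". The precedence rule in 3.1.5 protects a nominal visit only against End of Study/ET and End of Pegloticase data. It does not mention unscheduled draws.

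**Early stopping and other therapy**
- The estimand table in SAP 3.4.2.1 makes subjects non-responders if they meet the sUA discontinuation criterion or have fewer than two Month 6 visits with sUA. For other early stoppers, available Month 6 values are used. Restarted ULT is not named.
- Protocol 9.5.10: "re-introduction of oral ULTs should not start until after the End of Pegloticase Visit (or End of Study) laboratory tests are collected". The Protocol Synopsis, under Restricted Medications, lists ULT as prohibited for the study as a whole.

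**Cut-offs set elsewhere**
- SAP 3.5.1, for pharmacokinetics: "Concentrations more than 17 days after the last infusion will be excluded from the summary". SAP 3.6.4 and 3.6.5 stop laboratory and vital-sign summaries 30 days after the last dose.

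**The concern.** The endpoint is meant to describe urate control on pegloticase with methotrexate at the chosen infusion duration. The last infusion is at Week 22 (Day 155), and Protocol 7.2 says: "Pegloticase needs to be re-administered every two weeks to achieve optimal therapeutic outcomes and prevent elevations in sUA levels". An sUA drawn well after Week 24 says little about that. An sUA held down by allopurinol or febuxostat says nothing about pegloticase.

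The two gaps pull in opposite directions. Late off-drug values can lower the response rate, and ULT-controlled values can raise it. Two programmers following the SAP faithfully could also classify the same subject differently, and the choice would then be made after the data are visible.

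**Working it through.** The plan gives no figure for this endpoint. Its sample-size statement concerns infusion reactions and plays no part here, apart from supplying n = 110.

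**Inputs from the documents.** Target days 141, 155 and 169 for Weeks 20, 22 and 24, and the window limits (SAP Table 1); threshold 6 mg/dL and cut-off 80% (SAP 3.4.2.1); 110 subjects (SAP 1.1.3).

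**Assumed values.** sUA 0.5 mg/dL before the infusions at Days 141 and 155, 0.1 just after each, 1.0 at Day 169, and one unscheduled off-drug value of 9.

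**Window pattern.** Weeks 4 to 22 each run from target −6 to target +7 days. For Week 24 this gives 169 − 6 = 163 and 169 + 7 = 176. For comparison, the protocol's ±3 days gives Days 166 to 172, and the 17-day PK cut-off after Day 155 gives Day 172.

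**Late value.** Share = days with the curve below 6, divided by days from Day 141 to the end of the interval. A rise from *a* to 9 over *L* days stays below 6 for *L* × (6 − *a*)/(9 − *a*) days. Without the late value the share is 28/28 = 100%.

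| Handling of 9 mg/dL at Day 215 | Days below 6 | Interval | Share |
|---|---|---|---|
| Kept beside Day 169, actual date | 28 + 46 × 5/8 = 56.75 | 74 | 76.7% |
| Replaces Day 169, actual date | 14 + 60 × 5.9/8.9 = 53.8 | 74 | 72.7% |
| Replaces Day 169, placed at nominal Day 169 | 14 + 14 × 5.9/8.9 = 23.3 | 28 | 83.1% |
| Month 6 ends at Day 169 or 176 | 28 or 35 | 28 or 35 | 100% |

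The first two rows are non-response and the last two are response. With the 9 at Day 200 instead, keeping both values gives (28 + 31 × 5/8)/59 = 80.3% and replacement gives (14 + 45 × 5.9/8.9)/59 = 74.3%. Status again turns on the convention.

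**Restarted ULT, with no unscheduled draw needed.**
1. Last infusion at Week 18 (Day 127), stopped for a reason other than the sUA criterion.
2. The End of Pegloticase Visit is due within about two weeks. At about Day 141 it falls in the Week 20 window (135 to 148). For a last infusion at Week 20 (Day 141), a visit at about Day 155 falls in the Week 22 window (149 to 162).
3. Under Protocol 9.5.10, ULT may restart after those laboratory samples.
4. The scheduled Week 24 visit, 169 − 127 = 42 days after the last infusion (28 days for the Week 20 case), supplies the second Month 6 visit for the Week 18 stopper.

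Take 1 mg/dL at Day 141 for the Week 18 stopper. A Week 24 value of 9 without ULT gives 28 × 5/8 = 17.5 of 28 days, or 62.5%: non-responder. A value of 5 on ULT gives 100%: responder. For the Week 20 stopper, with 1 mg/dL at Day 155 and 9 at Week 24, the share is (14 + 14 × 5/8)/28 = 81.3% even without ULT. In this illustration, then, ULT decides the Week 18 case and not the Week 20 case.

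**Size.** One subject is 1/110 = 0.9 percentage points. An assumed 1 to 5 subjects would be 0.9 to 4.5 points.

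**The case against.** Several points on the other side are sound and limit what can be claimed.

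- A reader might infer that a late value must turn a true responder into a failure. The documents do not support that. Unscheduled values count only within Month 6, and Month 6 is three named visits. If the interval closes near Week 24, or the value is placed on nominal Day 169, the example subject stays a responder. What stands is that the SAP gives no end day and labels any value from Day 163 onward as Week 24.
- The replacement reading rests on a general reporting convention, whereas the specific responder text speaks of including unscheduled values. Adding the value is therefore the more natural reading, but the SAP does not say so.
- A reader might infer that any late local result enters. The same SAP section limits local values to pre-infusion samples with no central counterpart, and no infusion follows Week 22, so late local draws are largely excluded.
- Late values should be few. The 3-month visit is a separate nominal visit outside Table 1, and Week 24 and End of Study are one visit with a ±3-day allowance.
- A reader might infer that someone who stopped months earlier is readily credited as a responder. Such subjects attend follow-up visits only. A subject who stops at Week 8 normally has one Month 6 sUA and is a non-responder under the one-visit rule, unless an unscheduled draw is added.
- Using sUA after pegloticase has stopped is a stated estimand choice, the other cut-offs serve other purposes, and every visible window table ends open. The documents give no half-life, so the timing of washout is an assumption.

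None of this covers ULT. SAP 3.4 promises a composite strategy for binary responder endpoints, and crediting urate control achieved by another drug runs against it.

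**Conclusion.** The point holds as two gaps in specification. First, the Week 24 sUA window and the Month 6 interval have no end, so a late off-drug value can enter the endpoint; whether it changes status depends on a convention that the SAP leaves open. Second, sUA on restarted ULT is not set aside. The realistic case is a subject whose last infusion is at about Week 18 to 20 and who stops for a reason other than the sUA criterion.

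The severity is minor. The endpoint is secondary and descriptive, the primary infusion-reaction endpoint is untouched, and the bias can go either way. The number of subjects affected is not in the documents. At n = 110, 0.9 points per subject compares with an exact 95% interval about 18 to 19 points wide at assumed response rates of 42% to 70%. All sUA values in the examples are assumptions.

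**What to change.** SAP wording:

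1. In Table 1, close the Week 24 window for sUA at Day 176, following the pattern of Weeks 4 to 22, and end the Month 6 interval there.
2. In 3.1.7, state that an unscheduled sUA joins the curve at its actual date and does not replace a scheduled value.
3. In 3.4.2.1, name the start of oral ULT before the end of Month 6 as an intercurrent event under the composite strategy. sUA taken after that start is then not evidence of response, and a subject left with fewer than two qualifying Month 6 visits is a non-responder. Also say how the rest of Month 6 is counted when two qualifying visits precede ULT, as can happen after a last infusion at Week 20.

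The Protocol Synopsis (Restricted Medications) and Protocol 9.5.10 must also be reconciled on when ULT is prohibited.

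No new data are needed, because Protocol 9.5.9 already records medication start and stop dates. There is a cost. A completer whose Week 24 visit falls after Day 176 loses the interval after the last infusion. An early stopper with a visit that late may drop to one Month 6 visit and count as a non-responder. Both should be rare given the ±3-day visit window.

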### 3.1.8 Pooling of Centers

Data from sites will be summarized together for analyses

## 3.2 Handling of Missing Data

Aside from responder rates, where non-responder imputation is planned (see Exploratory Endpoints, [Section 3.4.3](#)), summary statistics will be computed for each efficacy endpoint using the Observed Cases (OC) with no imputation for missing data.

Unless otherwise specified, no other imputation of missing values will be done.

### 3.2.1 Medication Dates

For prior and concomitant medications with incomplete dates, the following rules will be used to impute start and/or stop dates for the purposes of determining if a medication is prior, concomitant in the MTX Run-in Period, or concomitant in the Pegloticase + MTX Period. Imputed dates will not be presented in the data listings.

For partial start dates:

- If the month and year are provided and day is missing, and the month and year match the month and the year of the first pegloticase dose date AND match the month and the year of the first MTX dose (i.e. the MTX and pegloticase started in the same month), the day of the first dose date of MTX will be imputed. Otherwise, if the month and year match the month and year of the first pegloticase dose date, then the first dose date of pegloticase will be imputed. Otherwise, if the month and year match the month and year of the first MTX dose date, then the first dose date of MTX will be imputed. Otherwise, the first of the month will be used.
- If the year is provided and the month and day are missing and the year matches the year of the first pegloticase dose date and the year matches the year of the first MTX dose date,

the month and day of the first MTX date will be imputed. Otherwise, if the year matches the year of the first dose of pegloticase, the first dose date of pegloticase will be imputed. Otherwise, if the year matches the year of the first MTX date, then the first dose date of MTX will be imputed. Otherwise, January will be used.

- If the start date is completely missing, the start date will not be imputed. If the stop date is after first dose date of pegloticase, the medication will be considered to be both prior, concomitant in the MTX Run-in Period, and concomitant in the Pegloticase + MTX Period. If the stop date is after the first dose date of MTX, but prior to the first dose date of pegloticase, the medication will be considered to be prior and concomitant in the MTX Run-in Period. If the stop date is prior to the first dose date of MTX, the medication will be considered to be prior only.
- If the stop date is complete and the imputed start date is after the actual stop date, then the start date will be imputed as the stop date.

For partial stop dates:

- If the month and year of stop are provided, but the day is missing, then the last day of the month will be used.
- If the year of stop is provided, but the month and day are missing, then December 31st of that year will be used.

If the stop date is completely missing, then the date of last study visit will be used.

